2.4 Determination of sample size

A total of 450 subjects will be randomly assigned in a 1:1:1 ratio to the following treatment groups:

- Bimekizumab 320mg Q4W throughout the study (150 subjects)
- Bimekizumab 320mg Q4W/Q8W (ie, bimekizumab 320mg Q4W until Week 16, then bimekizumab 320mg Q8W from Week 16 through Week 52 (150 subjects)
- Adalimumab 80mg administered as an initial dose, followed by 40mg Q2W starting 1 week after the initial dose (ie, adalimumab will be administered according to the labeling recommendations) until Week 24, then bimekizumab 320mg Q4W from Week 24 to Week 52 (150 subjects)

When comparing bimekizumab to adalimumab, the assumed responder rates for PASI90 and IGA at Week 16 for the bimekizumab group are 75% and 85%, respectively. These estimates are based on the results of the Phase 2b PS0010 study. The PASI90 responder rates at Week 16 for adalimumab from the VOYAGE-1 and VOYAGE-2 studies were 50% and 47%, respectively (Blauvelt et al, 2017; Reich et al, 2017). Additionally, the IGA responder rates at Week 16 for adalimumab in VOYAGE-1 and VOYAGE-2 were 66% and 68%, respectively. For the purposes of these sample size calculations at Week 16, we assume a PASI90 responder rate and IGA responder rate for adalimumab of 50% and 68%, respectively.

The testing procedure described in protocol Section 14.3 indicates that the first test will be to demonstrate noninferiority to adalimumab for the co-primary variables of PASI90 and IGA at Week 16. If non-inferiority for both tests is demonstrated, then superiority to adalimumab will be tested.

Because the superiority evaluation is the more stringent test, sample size calculations are based on the testing of superiority to adalimumab for PASI90 and IGA at Week 16. Given these assumptions and a sample size of 150 subjects in the adalimumab arm and 300 subjects in the pooled bimekizumab arms, the power to detect a statistically significant difference between bimekizumab and adalimumab is >99% for PASI90 response and 97% for IGA response. This

assumes a 2-sided significance level of 0.05. Because both co-primary endpoints are highly powered independently, and because PASI and IGA response tend to be highly correlated, the overall power for achieving superiority on both co-primary endpoints is not calculated here.

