10.2.1 Data considerations

Treatment-emergent AEs (TEAEs) are defined as those AEs that have a start date on or following the first dose of study treatment through the final dose of study treatment + 140 days

(covering the 20-week SFU period). If it is not possible (due to partial dates) to determine whether or not an AE is treatment-emergent then it will be assumed to be a TEAE.

The rules for imputing partial start or stop dates are outlined in Section 4.2.1.2.

If the intensity of an adverse event is unknown, it is considered as severe. If the relationship to study drug is missing, it is considered as related.

AEs will be presented as “number of subjects (percentage of subjects) [number of events]”. In this style of output, “[number of events]” will include all cases of an AE including repeat occurrences in individual subjects, while “number of subjects” will count each subject only once.

Subject time at risk represents the time a subject is at risk for having an AE. The definitions for subject time at risk (in days) are outlined in Section 10.1. These definitions will be used for exposure-adjusted AE summaries.

Selected AE summaries will include the exposure adjusted incidence rate (EAIR) with associated 95% confidence interval and the exposure adjusted event rate (EAER).

The EAIR is defined as the number of subjects (n) with a specific AE adjusted for the exposure and will be scaled to 100 patient-years:

$$EAIR = 100 \times n / \sum_{i=1}^N (T_{Exp(i)})$$

Where $T_{Exp(i)}$ is the exposure time and N is the number of subjects at risk.

If a subject has multiple events, the time of exposure is calculated to the first occurrence of the AE being considered. If a subject has no events, the total time at risk is used.

Exact Poisson 95% confidence intervals for incidence rates are calculated using the relationship between the Poisson and the Chi-square distribution (Ulm, 1990; Fay and Feuer, 1997):

$$LCL = \chi^2_{2n, \alpha/2} / 2$$

$$UCL = \chi^2_{2(n+1), \alpha/2} / 2$$

where n is the number of subjects with a specific AE for the incidence rate of interest and is the basis for the number of the degrees of freedom for the chi-square quantile for the upper tail probability χ^2 .

The EAER will be the number of AEs including repeat occurrences in individual subjects divided by the total time at risk scaled to 100 patient-years and calculated using:

$$EAER = 100 \times N_{AE} / \sum_{i=1}^N (T_{Risk(i)})$$

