where N_{AE} is the total number of AEs, T_{Risk} is the time at risk for each subject, and N is the total number of subjects at risk.

No confidence interval will be computed for EAER.

Selected summaries for the subjects who switch from adalimumab to bimekizumab will be presented by time of onset (≤ 70 days or > 70 days from the final dose of adalimumab). Only events starting after the first dose of bimekizumab will be included.

70 days was chosen as it is approximately equal to five half lives of adalimumab.

Selected summaries, as specified in Section 10.2.2, will include the risk difference between bimekizumab and adalimumab. The risk difference is calculated as:

$$RD = IP_{BKZ} - IP_{ADA}$$

where IP_{BKZ} is the incidence proportion for the bimekizumab-treated group and IP_{ADA} is the incidence proportion for the adalimumab group. Note that incidence proportion simply refers to the percentage of subjects within the specified treatment group that experienced a given adverse event.

The standard error for the risk difference is calculated as follows:

$$SE_{RD} = \sqrt{\left(IP_{BKZ} \times \left(\frac{1 - IP_{BKZ}}{n_{BKZ}} \right) \right) + \left(IP_{ADA} \times \left(\frac{1 - IP_{ADA}}{n_{ADA}} \right) \right)}$$

where n_{BKZ} is the number of subjects in the bimekizumab-treated group and n_{ADA} is the number of subjects in the adalimumab group.

The corresponding confidence interval for the risk difference is as follows:

$$CI_{RD} = RD \pm Z_{1-\alpha/2} \times (SE_{RD})$$

where $Z_{1-\alpha/2}$ is the Z statistic for the corresponding level of alpha. For the risk difference confidence intervals calculated in this SAP, 1.96 will be used (corresponding to a two-sided alpha of 0.05 and 95% confidence interval). Risk difference and the corresponding confidence interval will be presented as a percentage.

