10.2.2 AE summaries

The following summaries will be provided in five different ways: through Week 24 for the SS, through initial and maintenance treatment period for the BKZ Set, through initial treatment period for the SS, through the maintenance period for the MS (excluding patients randomized to ADA) and from Week 24 to Week 56 for the BKZ Week 24 Set for patients randomized to ADA switching to BKZ (to examine the events occurring within 70 days and >70 days of the treatment switch).

- Incidence of TEAEs – Overview
- Incidence of TEAEs per 100 subject years by SOC, HLT, and PT
- Incidence of Serious TEAEs per 100 subject years by SOC, HLT, and PT

The following summary will be provided in four different ways: through Week 24 for the SS, through initial and maintenance treatment period for the BKZ Set, through initial treatment period for the SS and through the maintenance period for the MS (excluding patients randomized to ADA).

- Incidence of TEAEs Leading to Discontinuation per 100 subject years by SOC, HLT, and PT

The following summaries will be provided in two different ways: through Week 24 for the SS, and through initial and maintenance treatment period for the BKZ Set:

- Incidence of TEAEs Leading to Death by SOC, HLT, and PT
- Incidence of TEAEs by Maximum Relationship by SOC, HLT, and PT
- Incidence of Serious TEAEs by Relationship SOC, HLT, and PT – Note: For EudraCT reporting purposes
- Incidence of Related Serious TEAEs by SOC, HLT, and PT
- Incidence of TEAEs Leading to Death by Relationship by SOC, HLT, and PT – Note: For EudraCT reporting purposes
- Incidence of TEAEs by Maximum Severity, SOC, HLT, and PT
- Incidence of TEAEs by decreasing frequency of PT
- Incidence of TEAEs Above Reporting Threshold of 5% by SOC and PT
- Incidence of Non-Serious TEAEs by SOC, HLT, and PT
- Incidence of Non-Serious TEAEs by Relationship SOC, HLT, and PT
- Incidence of Non-Serious TEAEs Above Reporting Threshold of 5% by SOC and PT
- Incidence of Non-Serious TEAEs Above Reporting Threshold of 5% by Relationship SOC and PT
- Incidence of Related TEAEs by SOC, HLT, and PT
- Incidence of Related TEAEs Above Reporting Threshold of 5% by SOC and PT

The following summary will be provided through Week 24 for the SS:

- Incidence of TEAEs Above Reporting Threshold of 5% with Risk Differences by SOC and PT
- Incidence of Serious TEAEs and Risk Differences by SOC and PT

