10.2.3 Other Safety topics of interest

The following are AEs of other safety topics of interest that require special statistical analyses. Along with the tables described, there will be a table which displays the risk difference and 95% confidence intervals for each of the topics of interest. A corresponding figure (with dot plots) will be prepared.

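### The Wald interval prescribed for adverse-event risk differences has no zero-event rule: it has zero width at 0 vs 0 events and can mislead when events fall in one arm only

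*SAP*

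**What the plan says.** SAP 10.2.1 defines the risk difference as the incidence proportion on bimekizumab minus that on adalimumab. It introduces the variance with "The standard error for the risk difference is calculated as follows" and gives the unpooled binomial form. The interval is the difference plus or minus a normal quantile times that standard error: "For the risk difference confidence intervals calculated in this SAP, 1.96 will be used", described as "corresponding to a two-sided alpha of 0.05 and 95% confidence interval". No continuity correction, score or exact method, or zero-event rule accompanies it.

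The interval has three uses. SAP 10.2.2 lists two risk-difference tables for the Safety Set through Week 24: TEAEs above a 5% threshold, and "Incidence of Serious TEAEs and Risk Differences by SOC and PT". It also asks for dot plots of these intervals. SAP 10.2.3 adds that "there will be a table which displays the risk difference and 95% confidence intervals for each of the topics of interest", again with dot plots. The topics in 10.2.3.1 to 10.2.3.8 include opportunistic infection, MACE, suicidal ideation and behavior, inflammatory bowel disease and anaphylaxis.

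For per-arm rates, SAP 10.2.1 takes a small-sample approach: "Exact Poisson 95% confidence intervals for incidence rates are calculated using the relationship" between the Poisson and chi-square distributions.

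**The concern.** An arm with no events has an estimated variance of zero, so it adds nothing to this standard error however small the arm is. If both arms have no events, the interval has zero width and reads as certainty of no difference. If only one arm has events, the other arm's uncertainty is left out altogether.

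Serious events by preferred term, and several of the topics, are where zero cells can be expected. These are also the only between-arm intervals planned for adverse events, and they are plotted. A reader could take a zero-width bar as proof of no difference, see a bimekizumab signal the data do not support, or overlook a difference they do support.

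**Working it through.** **Inputs.** The multiplier and the unpooled standard error come from SAP 10.2.1. Arm sizes come from SAP 2.4: "sample size of 150 subjects in the adalimumab arm and 300 subjects in the" pooled bimekizumab arms. The true event risks below are assumptions, since neither document gives expected rates for serious TEAEs or safety topics.

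**Plan's own figure.** The 97.5th normal percentile is 1.95996, which rounds to the stated 1.96. The SAP states no coverage figure to reproduce.

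**Formulas.** With a events of 300 on bimekizumab and b of 150 on adalimumab:

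- RD = a/300 - b/150
- SE = sqrt[p1(1-p1)/300 + p2(1-p2)/150]; Wald interval = RD ± 1.96 SE
- Newcombe combines the two single-arm Wilson intervals. With no events, the Wilson upper limit is z²/(n + z²).

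**No events in either arm.** SE = 0, so Wald is [0, 0]. The Wilson upper limits are 3.8416/303.8416 = 1.26% and 3.8416/153.8416 = 2.50%, so Newcombe is [-2.50%, +1.26%].

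**Events in one arm only.**

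- 4/300 vs 0/150: SE = sqrt(0.01333 × 0.98667/300) = 0.662%, and 1.333% ± 1.298%.
- 0/300 vs 3/150: SE = sqrt(0.02 × 0.98/150) = 1.143%, and -2.000% ± 2.240%.

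| Events | Wald | Newcombe | Fisher p |
|---|---|---|---|
| 4/300 vs 0/150 | +0.04% to +2.63% | -1.29% to +3.38% | 0.31 |
| 0/300 vs 3/150 | -4.24% to +0.24% | -5.71% to -0.17% | 0.04 |

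In both rows Wald and Fisher disagree about zero, in opposite directions; Newcombe agrees with Fisher in both.

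**Exact coverage.** Coverage is the sum of the binomial probabilities of all outcomes whose Wald interval contains the true difference (n = 300 and 150).

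| True risk, bimekizumab vs adalimumab | Coverage | P(0 vs 0) | Coverage given at least one event |
|---|---|---|---|
| 0.1% vs 0 | 25.9% | 74.1% | 99.99% |
| 0.25% vs 0 | 52.8% | 47.2% | 99.98% |
| 0.5% vs 0 | 77.7% | 22.2% | 99.9% |
| 0.98% vs 0 | 94.5% | 5.2% | 99.7% |
| 1% vs 0 | 79.9% | 4.9% | 84.0% |
| 1.5% vs 0 | 93.4% | 1.1% | 94.4% |
| 2% vs 0 | 93.2% | 0.2% | 93.4% |
| 0 vs 0.5% | 52.8% | 47.2% | 99.98% |
| 0 vs 1% | 77.8% | 22.2% | 99.9% |
| 0 vs 2% | 80.0% | 4.8% | 84.1% |

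The pattern can be checked by hand. At 0.25% vs 0, P(0 vs 0) = 0.9975^300 = 0.472, and 1 - 0.472 = 0.528 is essentially the whole coverage. At 1% vs 0 there is a second failure: the interval for 1/300 vs 0/150 stops at 0.986%, short of the true 1%. That outcome has probability 300 × 0.01 × 0.99^299 = 0.149; added to 0.049 for no events, it gives a miss of about 0.198. At 0.98% the one-event interval still reaches the truth, which is why coverage jumps rather than moving smoothly.

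**Common events.** Wald coverage is 94.6% at 5% vs 5% and 94.8% at 10% vs 5%.

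**The case against.** **The zero-event problem is one defect, not two, at the lowest rates.** This stands. At about 0.5% or below, coverage given at least one event is 99.9% or more; the shortfall is the chance of seeing nothing. In the serious-TEAE table, a preferred-term row would normally appear only if someone had the event. That is an assumption about layout, but if it holds, zero-width rows arise mainly among the pre-listed safety topics.

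**Uncertainty is shown elsewhere.** This partly stands. SAP 10.2.2 requires exposure-adjusted incidence rates with 95% intervals in every summary per 100 subject-years. With no events the exact Poisson upper limit is 3.69 events. If all subjects contribute 24 weeks, exposure is 300 × 168/365.25 = 138 years and 69 years, so the upper limits are about 2.7 and 5.3 per 100 subject-years. A reader would see these, but they are per arm and do not describe the difference.

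**The rates and setting are assumed.** This stands. No expected rates are given, and 10.2.3 states no period for the topic risk-difference table. Fungal infection, hypersensitivity and hepatic events are also topics, and nothing in the documents shows that they will be rare.

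**The intervals are descriptive.** This stands. They lie outside the fixed testing sequence in SAP 4.5 and drive no decision rule.

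None of this answers the zero-width interval itself, which needs no assumed rate, or the two one-arm examples, in which events were observed.

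**Conclusion.** The point holds. The prescribed interval is Wald without a zero-event rule, and it is applied to tables where zero cells can arise. It prints [0, 0] at 0 vs 0, and with events in one arm only it can err in either direction about zero. Under assumed risks confined to bimekizumab, coverage is about 53% at 0.25%, 78% at 0.5% and 80% at 1%, and about 93% at 1.5 to 2%. These figures rest on pooled arms of 300 vs 150.

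Three stronger readings are tempting and are not supported:

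- A reader might take a band such as 53 to 81% as the coverage of this plan. It depends on the chosen true rates. Other rare one-arm rates give anything from 26% to 94.5%, and coverage is not monotone in the rate.
- A reader might infer that these intervals are always far too narrow for a rare one-arm risk. At about 0.5% or below they over-cover once any event is seen; a real shortfall with events present appears at 1% vs 0.
- A reader might call these the only error bars on comparative safety. They are the only between-arm adverse-event intervals; the per-arm exact rate intervals remain.

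The table of TEAEs above 5% is essentially unaffected, and no confirmatory conclusion changes. The change is worth making because it corrects visible safety output at almost no cost.

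**What to change.** In SAP 10.2.1, replace the Wald interval for adverse-event risk differences with a score-type interval, Newcombe or Miettinen-Nurminen, and say that it also applies when one or both arms have no events. Use it in the 10.2.2 and 10.2.3 tables and in the dot plots. The point estimates do not change.

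The cost is one paragraph of SAP text and one program option. The drawback is that intervals for rare events become wider, asymmetric and somewhat conservative: Newcombe coverage is about 98 to 100% at the rare one-arm risks examined.

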10.2.2 AE summaries

The following summaries will be provided in five different ways: through Week 24 for the SS, through initial and maintenance treatment period for the BKZ Set, through initial treatment period for the SS, through the maintenance period for the MS (excluding patients randomized to ADA) and from Week 24 to Week 56 for the BKZ Week 24 Set for patients randomized to ADA switching to BKZ (to examine the events occurring within 70 days and >70 days of the treatment switch).

- Incidence of TEAEs – Overview
- Incidence of TEAEs per 100 subject years by SOC, HLT, and PT
- Incidence of Serious TEAEs per 100 subject years by SOC, HLT, and PT

The following summary will be provided in four different ways: through Week 24 for the SS, through initial and maintenance treatment period for the BKZ Set, through initial treatment period for the SS and through the maintenance period for the MS (excluding patients randomized to ADA).

- Incidence of TEAEs Leading to Discontinuation per 100 subject years by SOC, HLT, and PT

The following summaries will be provided in two different ways: through Week 24 for the SS, and through initial and maintenance treatment period for the BKZ Set:

- Incidence of TEAEs Leading to Death by SOC, HLT, and PT
- Incidence of TEAEs by Maximum Relationship by SOC, HLT, and PT
- Incidence of Serious TEAEs by Relationship SOC, HLT, and PT – Note: For EudraCT reporting purposes
- Incidence of Related Serious TEAEs by SOC, HLT, and PT
- Incidence of TEAEs Leading to Death by Relationship by SOC, HLT, and PT – Note: For EudraCT reporting purposes
- Incidence of TEAEs by Maximum Severity, SOC, HLT, and PT
- Incidence of TEAEs by decreasing frequency of PT
- Incidence of TEAEs Above Reporting Threshold of 5% by SOC and PT
- Incidence of Non-Serious TEAEs by SOC, HLT, and PT
- Incidence of Non-Serious TEAEs by Relationship SOC, HLT, and PT
- Incidence of Non-Serious TEAEs Above Reporting Threshold of 5% by SOC and PT
- Incidence of Non-Serious TEAEs Above Reporting Threshold of 5% by Relationship SOC and PT
- Incidence of Related TEAEs by SOC, HLT, and PT
- Incidence of Related TEAEs Above Reporting Threshold of 5% by SOC and PT

The following summary will be provided through Week 24 for the SS:

- Incidence of TEAEs Above Reporting Threshold of 5% with Risk Differences by SOC and PT
- Incidence of Serious TEAEs and Risk Differences by SOC and PT

The following summary will be provided through initial and maintenance treatment period for the BKZ Set:

- Incidence of TEAEs per 100 subject years by SOC, HLT, and PT and by Time of Onset Relative to Anti-bimekizumab Antibody Status

In addition, all summaries of TEAEs based on “100 subject years” should include EAIR (with 95% confidence interval) and EAER.

The tables with risk differences will also be accompanied by figures (dot plots) which show the incidence of the adverse events and corresponding 95% risk difference confidence intervals. These will be ordered by descending order of risk difference (bimekizumab vs adalimumab).

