5.8 Rationale for study design and selection of dose

5.8.1 Study design

A randomized, active-controlled study design has been selected to demonstrate efficacy and safety of bimekizumab for regulatory approval. The study population will include adults with moderate to severe chronic plaque PSO and allow subjects who have received previous biologic treatment as well as those who are biologic treatment naïve. The primary efficacy outcome measures (based on PASI and IGA) and other efficacy assessments included in this study are consistent with those used for other PSO studies and are considered appropriate for establishing efficacy of bimekizumab. An Initial Treatment Period of 16 weeks will be used to demonstrate the efficacy of bimekizumab compared with adalimumab. The study duration extends beyond the Initial Treatment Period (to 56 weeks) to allow for collection of long-term safety and efficacy data.

At Week 24, subjects on adalimumab treatment are re-allocated to treatment with bimekizumab 320mg Q4W. This allows for a controlled evaluation of the safety and efficacy of switching from a product with one mechanism of action to another, which is known to occur in clinical practice due to either loss of response or access. In a recent PSO study in which subjects were switched from adalimumab to a treatment with a different mechanism of action, there was no evidence of an increased safety risk following the switch without washout (Reich et al, 2017).

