14.5 Planned safety and other analyses

14.5.1 Safety analyses

Safety variables will be analyzed for all subjects in the SS. Additional summaries focusing on safety during the Maintenance Treatment Period will also be prepared and will be based on the RS.

Adverse events will be coded according to the Medical Dictionary for Regulatory Activities (MedDRA[®]). Adverse events will be summarized descriptively by treatment group, primary system organ class, High Level Term (HLT), and preferred term. Additional tables will summarize AEs by intensity and relationship to IMP, AEs leading to withdrawal from the study, SAEs, and deaths. Specific safety topics of interest will be summarized and will be described in greater detail in the SAP.

For subjects who switch treatment, AEs will be allocated to the treatment the subject was on the day the event occurred. If the event occurs on the day of the switch, it will be attributed to the initial treatment, unless the event has a HLT of “Injection Site Reactions”, in which case it will be attributed to the new treatment. Because the safety of switching from adalimumab to bimekizumab treatment is of particular interest, additional summaries to evaluate this will be specified in the SAP.

Laboratory values (including markedly abnormal labs), urinary values, vital signs, and extent of exposure will be presented descriptively by treatment group. Definitions for markedly abnormal laboratory values will be provided in the SAP.

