3.5.6 Bimekizumab Week 24 Set

The BKZ Week 24 Set will consist of all subjects who have received at least 1 dose of BKZ on or after Week 24.

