3.6 Treatment assignment and treatment groups

It is expected that subjects receive treatment as randomized and hence safety analyses will be based on the SS, as randomized. However, if after unblinding it is determined that subjects randomized to a treatment arm had never received such treatment, then for safety analyses, these subjects will be reallocated to the appropriate received treatment groups, unless otherwise specified.

Efficacy analyses should be performed according to randomized treatment and not actual treatment received.

Summaries based on SS or RS will be provided by “BKZ 320mg Q4W”, “BKZ 320mg Q4W/Q8W”, “BKZ Total” and “ADA” treatment groups. The ADA group will only be presented from Baseline to Week 24 in the by-visit summaries.

Summaries based on BKZ Week 24 set will be provided by “BKZ 320mg Q4W”, “BKZ 320mg Q4W/Q8W” and “ADA/BKZ 320mg Q4W” treatment groups for disposition, baseline assessments and efficacy. The ADA/BKZ 320mg Q4W group will be presented from Week 28 to Week 56 in the by-visit summaries for the PASI scores and the DLQI only.

For safety, summaries on the BKZ set will be provided by “BKZ 320mg Q4W”, “BKZ 320mg Q8W” and “BKZ Total”. BKZ Q4W will include data from subjects in the BKZ Q4W/Q8W arm (up to Week 16) and the ADA/BKZ Q4W arm (after Week 24).

Safety summaries on the BKZ Week 24 set will be provided for subjects switching from Adalimumab to Bimekizumab.

Summaries based on the Maintenance set will be provided by “BZK 320mg Q4W”, “BKZ 320mg Q4W/Q8W” and “BKZ Total”.

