10.1.4 Exposure during the maintenance period for BKZ Set

Definitions for study medication duration (days) and time at risk (days) during the Maintenance Period (Week 16 to Week 56) are provided as follows:

For subjects randomized to BKZ Q4W/Q4W or BKZ Q4W/Q8W:

Study medication duration (days)

- Date of last dose of bimekizumab in the Maintenance Period – date of first dose in the Maintenance Period + 28 days (or 56 days in the case of Q8W dosing).

Note: If date of last dose of bimekizumab in the Maintenance Period + 28 days (or 56 days in the case of Q8W dosing) extends to a date beyond the final visit date in the Maintenance Period (including PEOT, but not including SFU), then this calculation reverts to:

- Final visit date in the Maintenance Period (including PEOT, but not including SFU) – date of first dose in the Maintenance Period + 1.

Note: For subjects who die, if date of last dose of bimekizumab in the Maintenance Period + 28 days (or 56 days in the case of Q8W dosing) extends to a date beyond the date of death, then this calculation reverts to:

- Date of death – date of first dose in the Maintenance Period + 1.

Time at risk (days):

- For subjects who continue into an open-label study (and, therefore, do not have the SFU visit in the feeder study): Final visit date in the Maintenance Period – date of first dose in the Maintenance Period + 1.
- For subjects who die prior to the final visit in the Maintenance Period: Date of death – date of first dose in the Maintenance Period + 1.
- For all other subjects, use the minimum of the following:
 - Date of last dose in the Maintenance Period – date of first dose in the Maintenance Period + 140 days.
 - Date of last clinical contact – date of first dose in the Maintenance Period + 1.

Note: This group could include subjects who discontinue the maintenance period early, subjects who complete the Maintenance Period as scheduled but choose not to continue into an open-label study, or subjects who are ongoing in the SFU period at the time of the data snapshot.

For subjects randomized to ADA/BKZ Q4W:

Study medication duration (days)

Only the duration of Bimekizumab treatment will be derived over this period as the summaries produced are for the BKZ Set (not including any adalimumab treatment).

- Date of last dose of bimekizumab on or after Week 24 – date of first dose on or after Week 24 + 28 days

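### Adverse events over Weeks 24–56 are tabulated for adalimumab switchers only, with no bimekizumab column for the same window and no between-arm contrast after the switch

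*SAP*

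**What the plan says.** Protocol 5.8.1 says of the Week 24 switch: "This allows for a controlled evaluation of the safety and efficacy of switching from a product with one mechanism of action to another". Protocol 14.5.1 describes the safety of switching as of particular interest and states that "additional summaries to evaluate this will be specified in the SAP".

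SAP 3.5.6 defines the BKZ Week 24 Set as "all subjects who have received at least 1 dose of BKZ on or after Week 24", which takes in all three randomised arms. SAP 3.6 and SAP 8 show that set by all three arms for efficacy, and SAP 3.6 does so for disposition and baseline too. For safety, SAP 3.6 says: "Safety summaries on the BKZ Week 24 set will be provided for subjects switching from Adalimumab to Bimekizumab".

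SAP 10.2.2 produces the overview, TEAE and serious TEAE tables in five ways. The only one confined to the post-switch period runs "from Week 24 to Week 56 for the BKZ Week 24 Set for patients randomized to ADA switching to BKZ", and its stated purpose is to separate events within 70 days from later ones. A further version runs "through the maintenance period for the MS (excluding patients randomized to ADA"), and SAP 10.1.4 defines that period by the words "during the Maintenance Period (Week 16 to Week 56"). In the BKZ Set version, SAP 3.6 builds the BKZ Q4W column from the Q4W arm, the Q4W/Q8W arm up to Week 16 "and the ADA/BKZ Q4W arm (after Week 24"). TEAEs leading to discontinuation come in four ways; the switcher version is the one left out. The AE tables with risk differences listed in SAP 10.2.2 run through Week 24 only.

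**The concern.** To judge whether switching carries added risk, a reader needs to know how often events occur over the same period in people who did not switch. The trial has such people: under Protocol 7.2, the Q4W/Q4W arm and the switchers receive the same injections from Week 24 to Week 52. The plan tabulates efficacy for these groups together but adverse events for the switchers alone, and gives no reason for the difference.

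The reader is left to carry the switchers' figures across to a table with another window. If event rates change over the study or with time on drug, that comparison can suggest a risk, or an absence of risk, that switching did not cause. Discontinuations due to adverse events are a natural place for a switching problem to appear, and here the switchers cannot be seen separately in the AE tables.

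**Working it through.** The plan gives no figure on this point, so the check has two parts: lining up the windows, then asking what a mismatch could do.

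**Windows of the AE tables (SAP 3.6, 10.1.4, 10.2.2)**

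| Table | Weeks | Contents |
|---|---|---|
| Safety Set, initial period | 0–16 | bimekizumab arms and adalimumab |
| Safety Set, through Week 24 | 0–24 | bimekizumab arms and adalimumab |
| BKZ Set | 0–56 | Q4W column pools three sources, switchers included |
| Maintenance Set | 16–56 | Q4W, Q4W/Q8W, total; adalimumab arm excluded |
| BKZ Week 24 Set | 24–56 | switchers only |

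No bimekizumab column matches Weeks 24–56. The Maintenance Set Q4W column contains all 32 switcher weeks plus 8 more: 32/40 = 80% overlap.

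**Switchers inside the BKZ Set Q4W column.** Planned arm-weeks are 56 (Q4W) + 16 (Q4W/Q8W) + 32 (switchers) = 104. The switchers' share is 32/104 = 31%. This assumes equal arms and full retention.

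**Effect on exposure-adjusted rates with no switching effect.** Assume the event rate is k times higher early and 1 later, with k = 1.25, 1.5 or 2. These values are assumptions; the documents support none of them. Two readings of early are possible.

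*Early means before study Week 24.*
- Switchers: 1.
- Maintenance Set Q4W: (8k + 32)/40 = 1.05, 1.10, 1.20.
- BKZ Set Q4W: (40k + 64)/104 = 1.10, 1.19, 1.38.
- Q4W/Q4W Weeks 24–56: 1.
- Q4W/Q4W Weeks 0–32: (24k + 8)/32 = 1.19, 1.38, 1.75.

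*Early means the first 24 weeks on bimekizumab.*
- Switchers: (24k + 8)/32 = 1.19, 1.38, 1.75.
- Maintenance Set Q4W: 1.05, 1.10, 1.20, as before.
- BKZ Set Q4W: (64k + 40)/104 = 1.15, 1.31, 1.62.
- Q4W/Q4W Weeks 24–56: 1.
- Q4W/Q4W Weeks 0–32: the same as the switchers.

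Dividing the switchers' rate by each comparator shows how they would appear:

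| Comparator | Rate follows study week | Rate follows time on bimekizumab |
|---|---|---|
| Maintenance Set Q4W | 5%, 9%, 17% lower | 13%, 25%, 46% higher |
| BKZ Set Q4W | 9%, 16%, 28% lower | 3%, 5%, 8% higher |
| Q4W/Q4W Weeks 24–56 | no difference | 19%, 38%, 75% higher |
| Q4W/Q4W Weeks 0–32 | 16%, 27%, 43% lower | no difference |

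The last two rows each remove one source of error and leave the other.

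**Unadjusted percentages.** The overview table is not labelled per 100 subject years, so the SAP does not require exposure adjustment there. At an assumed constant 1 first event per patient-year, incidence is 1 − exp(−32×7/365.25) = 45.8% over 32 weeks and 1 − exp(−40×7/365.25) = 53.5% over 40 weeks, a gap due to window length alone.

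**Precision.** With full retention each arm contributes 150 × 32 × 7/365.25 = 92 patient-years. The 95% half-width for a risk difference of 150 versus 150, 1.96 × √(2p(1 − p)/150), is 3.2, 4.9, 10.4 and 11.3 percentage points at assumed incidences of 2%, 5%, 30% and 50%.

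**The case against.** The strongest reply is that a comparator already exists. The Maintenance Set Q4W column is a concurrent arm formed by randomisation, on the same dosing as the switchers from Week 24. It covers every switcher week, and its per-100-subject-years tables carry exposure-adjusted incidence and event rates. That stands: a reader might infer that switch safety has no control at all, and the documents do not support that.

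The switcher table also has a purpose of its own. SAP 10.2.1 explains that 70 days is about five half-lives of adalimumab, so the split examines carry-over within the arm. SAP 10.3 adds laboratory shift tables with the switchers beside the bimekizumab arms and a 70-day split for markedly abnormal values, and SAP 10.4.5 adds PHQ-9 for switchers. Protocol 14.5.1 promised further summaries without naming their form, and Protocol 5.8.1 is design rationale. It would therefore go too far to say that the SAP breaks a commitment. But the 70-day split cannot say what would have happened without a switch.

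Nor are discontinuation TEAEs missing for switchers altogether: they are counted in the BKZ Set Q4W column, and SAP 5.1 summarises discontinuations due to AEs for that set up to Week 56. What is missing is a separate switcher table.

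Finally, the obvious concurrent comparator can mislead. If rates fall with time on bimekizumab, it makes switchers look worse by up to 75% in the example with no switching effect. This objection stands, and it is why one added column is not enough. The precision argument also has force: with an assumed 75 first events, the Poisson half-width is about 1.96/√75 = 23%, wider than the 5–17% Maintenance Set figures. Imprecision does not, however, justify a mismatched window.

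**Conclusion.** The point holds in a limited form. Post-switch adverse events have no same-window comparator column and no between-arm contrast. The nearest comparator sits in a separate table with 80% overlap, and the BKZ Set Q4W column is unsuitable because about 31% of its planned arm-weeks belong to the switchers. Discontinuation TEAEs are not shown separately for them.

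The 5–28% figures should not be read as expected bias. They apply only if rates vary by study week, rest on assumed ratios, and reverse direction if rates vary by time on bimekizumab. The shares assume full retention, and membership of the BKZ Week 24 Set depends on still being dosed at Week 24, so even the concurrent comparison is not strictly by randomisation.

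These are descriptive safety tables, and no primary or multiplicity-controlled result is affected. The change is a cheap improvement that lets the trial address a question its protocol raises.

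**What to change.** In SAP 3.6 and 10.2.2:

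- Produce the Week 24–56 overview, TEAE and serious TEAE tables for all three arms of the BKZ Week 24 Set, and add TEAEs leading to discontinuation. Count events and time at risk from the first dose on or after Week 24, a date SAP 10.1.2 already uses.
- Keep the 70-day split for switchers.
- Show two Q4W/Q4W columns beside the switchers: Weeks 24–56, matched on study time, and the first 32 weeks of treatment, matched on time on drug. Both should be required. Draw the second from all treated Q4W/Q4W subjects, because limiting it to those still dosed at Week 24 would drop anyone who stopped early for an adverse event.
- Add a footnote that neither column matches on both scales, so a difference is attributed to switching only if it appears against both. This governs interpretation only; all differences are still reported.

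The cost is SAP wording, extra columns and one extra table, with no new data. The drawback is two imperfect comparators to interpret, and a real effect may show clearly against only one of them.
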